### Section Aa: Title & PI

#### A1. Main Title

A RANDOMIZED COMPARISON OF ULTRASOUND GUIDED SUPRACLAVICULAR BLOCK AND GENERAL ANESTHESIA TO IV NARCOTICS AND GENERAL ANESTHESIA FOR POSTOPERATIVE PAIN RELIEF IN CHILDREN WITH SUPRACONDYLAR FRACTURES

#### A3a. Financial Conflict of Interest

Does any member of study personnel (Investigator (including investigator's spouse and/or dependent children)) that are involved in the design, conduct, or reporting of the research have a Significant Financial Interest (SFI) that would reasonably appear to be affected by the research for which funding is sought and/or associated with an entity/business that would reasonably appear to be affected by the research?

No

#### **A5. Funding Source:**

Baylor College of Medicine (Internal Funding Only)

#### **A6a. Institution(s) where work will be performed:**

TCH: Texas Children's Hospital

#### **A6b. Research conducted outside of the United States:**

Country:  
 Facility/Institution:  
 Contact/Investigator:  
 Phone Number:

If documentation of assurances has not been sent to the Office of Research, please explain:

#### **A7. Research Category:**

#### **A8. Therapeutic Intent**

Does this trial have therapeutic intent?

No

#### **A9. ClinicalTrials.gov Registration**

Does this protocol/trial require registration on ClinicalTrials.gov due to it: meeting the definition of an Applicable Clinical Trial, being required under the terms and conditions of an award, or being proposed to be published in ICMJE journals?

Yes

Who will be responsible for registering and maintaining the registration of this Applicable Clinical Trial?

The BCM PI will register the trial because either:

- the trial is BCM PI-initiated,
- BCM is the lead site of this multicenter trial, or,
- the industry sponsor has instructed the BCM PI to register the trial, or,
- registration of this trial is required as a term and condition of the award by the funding agency.

ClinicalTrials.gov Identifier:

NCT02056288

## Section B: Exempt Request

### B. Exempt From IRB Review

Not Applicable

## Section C: Background Information

Supracondylar fracture of the humerus is a very common traumatic injury in pediatric orthopedic practice, accounting for more than half of all elbow fractures and roughly 33% of all pediatric limb fractures. They are classified into 3 types depending on the degree of displacement. Type 1 fractures have no or minimal displacement and can be managed with splinting and casting. However, surgical manipulation via closed reduction and percutaneous pinning with cast placement is usually required in type 2 supracondylar and lateral condyle fractures. Significant tissue interposition in type 3 supracondylar fractures may require an open operation for fracture reduction. These procedures all require general anesthesia, but postoperative pain can delay discharge, increase anxiety, and decrease satisfaction by the patient and parent. In addition, the treatment of pain with parenteral opioids can be associated with side effects like nausea, vomiting, respiratory depression and dysphoria. In adults, regional anesthesia with brachial plexus nerve block provides excellent analgesia while avoiding the side effects of opioids. However, until recently these nerve blocks were not often placed in pediatric patients because of concerns that improper positioning of the needle would result in low success rates, potential injury and toxicity from local anesthetics. Surgeons are also extremely concerned that analgesia from nerve blocks would hinder early diagnosis of a compartment syndrome at the site of injury, increasing the potential for long term injury. Compartment syndrome has an incidence of 0.1-0.3% based on a recent retrospective analysis with the main factor on presentation being a poorly perfused extremity and absent pulses. There are no case reports confirming that this has occurred in children receiving regional analgesia. The recent development of ultrasound guided nerve blocks has permitted a more precise visualization of the needle position and spread of local anesthetics, thus increasing the success rate with lower doses of local anesthetic and reducing needle trauma. Supraclavicular and infraclavicular ultrasound guided blocks of the brachial plexus are relatively easy to perform and have been shown to decrease the time to first rescue analgesia in a retrospective case review. Over 50 brachial plexus blocks have been performed in this patient population during the last 6 months at the Texas Children's Hospital, with the other patients receiving IV analgesia. However, there are no prospective data to show the benefits of brachial plexus blockade over systemic analgesia in children with supracondylar fractures.

## Section D: Purpose and Objectives

The primary hypothesis to be tested in this study is that ultrasound guided nerve block would result in better and more prolonged postoperative analgesia reflected by lower pain scores through the study. The study is designed as a prospective, randomized, patient and observer-blinded comparison between light sevoflurane anesthesia combined with ultrasound guided supraclavicular nerve block and general anesthesia combined with standardized postoperative systemic analgesia, in children undergoing closed reduction with percutaneous pinning of supracondylar humerus fractures.

## Section E: Protocol Risks/Subjects

### E1. Risk Category

Category 2: Research involving greater than minimal risk, but presenting the prospect of direct benefit to the individual subjects.

### E2. Subjects

Gender:

Both

Age:

Adolescent (13-17 yrs), Child (3-12 yrs)

Ethnicity:

All Ethnicities

Primary Language:

English, Spanish

Groups to be recruited will include:

Patients

Which if any of the following vulnerable populations will be recruited as subjects?

**Children**

Vulnerable populations require special protections. How will you obtain informed consent, protect subject confidentiality, and prevent undue coercion?

Subjects/parents/guardians will be approached in the waiting area on the day of surgery prior to the start of the procedure.

The study will be verbally explained with emphasis on the voluntary nature of study participation. A written consent form will be provided with ample time given to consider the study. A translator will be available for Spanish speakers.

Participants will be assured that every effort will be made to protect privacy and to prevent breach of confidentiality.

**E3. Pregnant woman/fetus**

Will pregnant women and/or fetuses (as described in 45 CFR 46 Subpart B) be enrolled in the research?

No

**E4. Neonates**

Will neonates of uncertain viability or nonviable neonates (as described in 45 CFR 46 Subpart B) be enrolled in the research?

No

**E5. Children**

Will children be enrolled in the research?

Yes

**Section F: Design/Procedure****F1. Design**

Select one category that most adequately describes your research:

y) Drug, Phase IV, Single Center

Discuss the research design including but not limited to such issues as: probability of group assignment, potential for subject to be randomized to placebo group, use of control subjects, etc.

randomized, observer-blinded comparison between light sevoflurane anesthesia combined with ultrasound guided supraclavicular nerve block and general anesthesia combined with standardized postoperative systemic analgesia

Inclusion Criteria:

(1) Supracondylar fracture (2) Age 2-17 years (3) American Society of Anesthesiologists Status 1 -3 (4) Scheduled for closed reduction with percutaneous pinning under general anesthesia

Exclusion Criteria:

(1) Pulseless extremity (2) Compromised neurologic status on exam (specifically assessment of radial, ulnar, and median nerve) (3) Known allergy to local anesthetics (7) Not scheduled for closed reduction with percutaneous pinning under general anesthesia (4) Bleeding diathesis (5) ASA status 4 or higher. (6) Sleep apnea by polysomnography

**F2. Procedure**

Written consent will be obtained by the investigators prior to the surgical procedure using the IRB approved consent form. The medical record will be examined and the use of any analgesic medications in the 24 hours prior to the procedure will be recorded. Patients will be taken to the OR and anesthetized using standard procedures of the Texas Children's Hospital (TCH) department of anesthesia, including monitoring according to the American Society of Anesthesiologists guidelines (EKG, pulse oximetry, BP, temperature and end-tidal expired carbon dioxide and inhalation anesthetic gases). If the Attending Anesthesiologist believes the child is at risk for aspiration of gastric contents, a rapid sequence induction with propofol 3-4 mg/kg and succinylcholine 1mg/kg IV will be performed with cricoid pressure, in keeping with standard practices. In other patients an IV will be started after induction of anesthesia. An age appropriate endotracheal tube or appropriate sized LMA will be inserted in all patients. Anesthesia will be maintained with sevoflurane, nitrous oxide and oxygen, adjusted to keep blood pressure and heart rate within 20% of baseline values, in keeping with standard practices. All patients will receive ketorolac 0.5mg/kg IV.

Patients will be randomized in a 1:1 ratio into one of two study groups: ultrasound guided supraclavicular block or IV opioids, based on a computer generated random number by using Random Allocation Software For Parallel Group Randomized Trials. The assignment will be made only after written informed consent has been obtained. There will be an equal chance a child will be assigned to one of the two groups. Patients randomized to the systemic analgesia group will receive 1mcg/kg of fentanyl IV after induction. Patients randomized to the supraclavicular block group will receive an ultrasound guided nerve block with 0.2 ml/kg ropivacaine 0.5% (maximum 10 ml), using the technique described by Marhofer et al. In order to decrease variance in success rates, the ultrasound guided nerve block will be performed by the Regional Anesthesia team. The Regional Anesthesia team has become well established at Texas Children's Hospital and all members of the team have successfully performed >100 ultrasound guided supraclavicular blocks in the past. Supraclavicular blocks were performed using the higher frequency of the probe and placing it in a coronal-oblique-plane in

the supraclavicular fossa. The brachial plexus will be identified as a cluster of hypoechoic nodules, lateral to the round pulsating hypoechoic subclavian artery and lying on top of the hyperechoic first rib. The cupola of the lung will be identified. If the transverse colli artery is visualized cephalically surrounding the plexus, the probe will be moved toward a better coronal oblique plane, directing the ultrasound beam slightly caudally, in order to keep the artery away from the plexus. The needle will be carefully introduced using an in-plane (IP) technique from lateral to medial, toward but not into the brachial plexus. The entire needle image will be visualised at all times to ensure it does not enter the vessel, nerve plexus or pleura. The spread of local anesthetic to all targets of the plexus will be observed on the ultrasound image.

The time taken to place the block will be recorded from the time the ultrasound probe is first placed on the child until completion of local anesthetic injection. The observer collecting postoperative data will not be present when the block is placed, and a band-aid will be placed over the supraclavicular fossa in all patients to maintain blinding of the observer to the group assignment. During the operation patients can receive intraoperative fentanyl, 1 mcg/kg IV at a time, if the attending anesthesiologist believes it is clinically indicated. At the end of the operation, anesthetic gases will be discontinued while the patient breathes 100% oxygen. The trachea will be extubated when the patient responds to commands, and the child will then be taken to the Post Anesthetic Care Unit (PACU) in keeping with standard practices. A validated pain scale (verbal rating scale where 0 = no pain and 10 = worst possible pain ever) will be used throughout to assess the severity of pain in the postoperative period. In keeping with current practice, patients with pain scores >4 will be treated with morphine 0.05mg/kg IV at 10 minute intervals until the score is below 4. Oral acetaminophen with hydrocodone (Lortab elixir 0.15mg/kg hydrocodone) will be administered to children for pain scores between 2-3. Supplemental oxygen, rescue antiemetic and antipruritic drugs will be administered in keeping with standard practices of TCH and the clinical judgment of the Attending Anesthesiologist. The duration of supplemental oxygen therapy, any medication administered and complications (side effects such as nausea, vomiting, itching, respiratory depression, prolonged awakening) will be recorded on the case report form.

The blinded observer will record pain scores within 15 minutes of arrival in the PACU and at 30 minutes, 1,2,6,12,24, and 48 hours after arrival in the PACU. If the child is sleeping at this time, the scores will be recorded when awake. The observer will also document any additional medication, the dose and the time given.

Prior to discharge home, parents will be educated on use of the 0-10 pain scale and given a diary to keep an accurate record of postoperative pain issues through the study period. The goal is to capture maximum pain scores at rest and with movement. Patient and parental satisfaction with pain management and with the global perioperative experience will also be graded on a numeric scale 0-10 scale.

Time to readiness for discharge will also be measured from the time the patient enters the PACU to when the patient attains an Aldrete score of 9-10. This is a standardized scale used to assess discharge readiness at TCH and is listed below:

Aldrete Scoring System Activity Can move voluntarily or on command 4 extremities 2 2 extremities 1 0 extremities 0  
 Respiration Can deep-breathe and cough freely 2 Dyspnea, shallow or limited breathing 1 Apneic 0 Circulation  
 Preoperative BP (mmHg) BP  $\pm$  20 mmHg of baseline 2 BP  $\pm$  20-50 mmHg of baseline 1 BP  $\pm$  20 mmHg 0 Consciousness  
 Fully Awake 2 Arousalable on calling 1 Not responding 0 Color Normal 2 Pale, dusky, blotchy 1 Cyanotic 0 Score of 10: ready for discharge

If the patient is discharged before the end of a 48 hour period after surgery, they will be given a diary to complete to list all medications given, and to assess their pain at various time intervals (12,24, 48 hours after surgery), along with their satisfaction with pain control. The patient will be contacted after discharge to obtain the data in the diary. Phone calls will also be placed on POD #1,2, & 3 to the family following to assess measured endpoints (pain, medication usage, satisfaction, resolution of nerve block). We will examine the differences in subjects who did or did not return the diaries regarding group assignments, age, gender, ASA physical status, duration of surgery, intraoperative opioids medications, time of the PACU stay, mean and peak pain scores and recorded opioid consumption in the PACU before discharge.

At the time of their follow up visit to the surgeon, a complete physical examination will be done including a neurological evaluation for any nerve injury.

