## Section G: Sample Size/Data Analysis

### G1. Sample Size

How many subjects (or specimens, or charts) will be used in this study?

Local: 188 Worldwide: 188

Please indicate why you chose the sample size proposed:

In a retrospective IRB approved study, the peak pain scores in the PACU were  $2.8 \pm 2.9$  in the group receiving systemic analgesia without a regional block. A group size of 34 would have an 80% power of detecting a clinically relevant difference in the peak pain scores of 2 at the 0.05 level of significance, assuming the same SD in pain scores in the treatment group. We will recruit 40 patients in each group to allow for dropouts and incomplete data. This group size would

have a 90% power of detecting a 75% increase in time to first analgesia in the regional anesthesia group compared to the IV analgesia group, based on the retrospective study.

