## G2. Data Analysis

Provide a description of your plan for data analysis. State the types of comparisons you plan (e.g. comparison of means, comparison of proportions, regressions, analysis of variance). Which is the PRIMARY comparison/analysis? How will the analyses proposed relate to the primary purposes of your study?

The primary endpoint of the study will be the peak or maximum pain score in the postoperative period. The secondary endpoints in the study will include (1) Opioid consumption in morphine equivalents (2) Time to first analgesia request (3) Time to achieving discharge readiness (4) Incidence of side effects such as vomiting, respiratory depression, itching, dysphoria, compartment syndrome (5) Patient and parental satisfaction. In order to keep the statistical analysis robust, we will also examine the differences in subjects who did or did not return the diaries regarding: a. group assignments b. age c. gender d. ASA physical status e. duration of surgery f. intraoperative opioids medications g. time of the PACU stay h. mean and peak pain scores and i. recorded opioid consumption in the PACU before discharge. These are known factors k that affect postoperative pain and failure to show a difference in these factors may suggest that the missing 48 hour data can be considered to be missing at random. We will also examine the PACU pain and opioid consumption data(first 2 hr after surgery) for all cases and separately for cases where the diaries were returned with the 48 hour data. If the conclusions regarding the secondary endpoints of pain in the PACU were not altered and the known factors affecting postoperative pain did not differ between those who did and did not return the diaries, it may suggest the conclusions are still robust. Our current plan will be modified to include not only daily phone calls from researchers, but Epic Mychart as well for protected email communication to better gather data.

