Descriptive statistics will be used for each group. The peak and mean pain scores, age, weight, opioid consumption, time to first analgesia and discharge readiness and satisfaction scores will be compared between the two groups using Students t test if the data is normally distributed, and nonparametric tests if the data are skewed. A Fisher's exact test or a Chi Square test with Yates correction will be used to compare the number of patients in each group with side effects as listed above. P values of <0.05 will be considered to be statistically significant.

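### No pre-operative pain score is planned and the primary peak-pain comparison is unadjusted, so the trial gives up some precision; the stated sample size and the test itself are sound.

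*Combined protocol and SAP*

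**What the plan says.** **Endpoint.** G2: "The primary endpoint of the study will be the peak or maximum pain score in the postoperative period".

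**When pain is scored.** F2 says that the 0-10 verbal rating scale "will be used throughout to assess the severity of pain in the postoperative period"; no other period is mentioned. The schedule is: "The blinded observer will record pain scores within 15 minutes of arrival in the PACU and at 30 minutes, 1,2,6,12,24, and 48 hours". No pre-operative time point appears there or elsewhere.

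**What is collected before surgery.** F2 has the medical record examined, and "the use of any analgesic medications in the 24 hours prior to the procedure will be recorded". Families are met before the operation, when the study is explained and consent is taken (E2, J2).

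**Teaching of the scale.** The only teaching described in F2 is for the take-home diary: "Prior to discharge home, parents will be educated on use of the 0-10 pain scale".

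**Primary test.** G2 says that peak scores, along with other continuous measures, "will be compared between the two groups using Students t test if the data is normally distributed, and nonparametric tests if the data are skewed". No covariate is named.

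**Sample size.** G1 takes a PACU peak score of 2.8 with SD 2.9 from a retrospective study of children without a block. It gives 34 per group for 80% power to detect a difference of 2, and raises this to 40 per group for dropouts. The same section states a total of 188 subjects.

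**The concern.** In a pain trial the natural covariate is the same score taken before treatment. Every child here has a fracture, is seen before surgery and has the chart opened for analgesics, so the score could be had at a contact that already exists.

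Children aged 2 to 17 are to be scored on one verbal scale, and the planning SD (2.9) exceeds the mean (2.8). Part of that spread plausibly reflects stable differences in pain level and in how children use the scale. A pre-operative score would remove whatever part it predicts. Without one, and with no other covariate in the test, all of the spread stays in the error term.

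At stake are interval width and power. A pre-operative score also cannot be recovered reliably once the trial is over, so the choice has to be made in the protocol. G2 plans to compare children who did and did not return diaries on factors that affect postoperative pain. Pre-operative pain could join that list only if it is collected.

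**Working it through.** **Inputs from G1:** difference 2; SD 2.9 in both arms; alpha 0.05; 34 per group, raised to 40; 188 in total, which is 188/2 = 94 per group under the 1:1 allocation in F2. Sidedness is not stated. Two-sided reproduces the plan's figure; one-sided would need only 26 per group.

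**Input not in the documents:** the correlation r between pre-operative score and peak postoperative score. A range of 0.2 to 0.5 is assumed.

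**Step 1: reproduce the plan's figure.** The normal-approximation formula is

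n = 2 × (1.960 + 0.842)² × 2.9² / 2² = 33.004, rounded up to 34 per group.

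Check with the noncentral t at 34 per group: standard error = 2.9 × √(2/34) = 0.703; noncentrality = 2/0.703 = 2.84; power = 80.0%. The plan's figure is correct and uses the full SD, as an unadjusted test requires.

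**Step 2: effect of adjustment.** With a baseline covariate the residual SD is 2.9 × √(1 − r²):

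- r = 0.2: 2.84
- r = 0.3: 2.77
- r = 0.5: 2.51

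The 95% interval half-width is t × residual SD × √(2/n), with t = 1.997, 1.991 and 1.973 for n = 34, 40 and 94. The few degrees of freedom used by covariates are ignored.

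| n per group | r | Power | Half-width |
|---|---|---|---|
| 34 | 0 (as planned) | 80.0% | 1.40 |
| 34 | 0.2 | 81.6% | 1.38 |
| 34 | 0.3 | 83.6% | 1.34 |
| 34 | 0.5 | 89.9% | 1.22 |
| 40 | 0 (as planned) | 86.1% | 1.29 |
| 40 | 0.2 | 87.5% | 1.26 |
| 40 | 0.3 | 89.1% | 1.23 |
| 40 | 0.5 | 94.0% | 1.12 |
| 94 | 0 (as planned) | 99.7% | 0.83 |
| 94 | 0.2 | 99.8% | 0.82 |
| 94 | 0.3 | 99.9% | 0.80 |
| 94 | 0.5 | 99.97% | 0.72 |

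**Step 3: the same gain in children.** The equivalent unadjusted group size is n/(1 − r²). For n = 34 this is 34/0.96 = 35.4 (r = 0.2), 34/0.91 = 37.4 (r = 0.3) and 34/0.75 = 45.3 (r = 0.5). Adjustment is thus worth about 1, 3 or 11 extra children per group.

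**Step 4: interval width at any n.** The proportional narrowing is 1 − √(1 − r²): 2% at r = 0.2, 5% at r = 0.3 and 13% at r = 0.5.

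**The case against.** **Nothing in the plan is wrong.** The test matches its sample size calculation, and randomization keeps the unadjusted comparison valid. This stands. A reader might infer that the missing baseline biases the result or leaves the trial short of its stated power. The documents support neither: the 80% was computed on the unreduced SD.

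**The gain rests on an assumed correlation.** This stands too. There is reason to expect a low value. The pre-operative score reflects an unreduced fracture under varying analgesia. The outcome is a peak after fixation, ketorolac for all and either block or fentanyl, with rescue morphine available, and an effective block could weaken the correlation in that arm. At r = 0.1 power at 34 per group is only 80.4%.

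**At 188 subjects the power argument disappears.** Correct; only the narrower interval remains. G1's conflict between 188 and 2 × 40 = 80 is a separate matter, but it decides how much this point is worth.

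**The missing score is not the only cause.** Age and analgesic use in the prior 24 hours are already recorded and could be adjusted for without new data. This stands, and the fix uses age.

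**A tempting stronger reading concerns teaching.** Because F2 mentions teaching the scale only before discharge, a reader might infer that children first meet it while waking from anesthesia, which would add noise to the endpoint. The text does not say so. That teaching is of parents, for the diary; whether children were shown the scale earlier is not stated. F2 also describes score-based rescue as current practice, has sleeping children scored once awake, and the endpoint is a maximum over repeated assessments.

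**A linear model suits this score poorly.** A bounded score with SD above its mean is likely to be skewed, and G2 already provides a nonparametric fallback. An adjusted analysis needs an equivalent provision.

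**Conclusion.** The point holds as a loss of precision that can be recovered cheaply. It is not an error in the sample size or in the test. Its size ranges from negligible to useful: 1.6 to 9.9 percentage points of power at 34 per group, 1.4 to 7.9 at 40 per group, and almost none at 94 per group, where the interval narrows by 2% to 13%.

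These figures assume r between 0.2 and 0.5, a two-sided test and a score obtained for nearly every child; missing baselines pull the effective correlation down. They also carry the SD of the PACU peak over to the peak across the whole postoperative period, as the plan's own calculation does.

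**What to change.** **F2.** At the pre-operative consent contact, show the 0-10 scale to child and parent and record one current pain score with its time. If the child cannot give one, take the last charted score when the record is examined for analgesics.

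**G2.** Prespecify the primary comparison of peak pain as a model with arm, pre-operative score and age. Fill absent baselines with the overall mean and add a missing indicator, so that no child is dropped. If the data are skewed, use a rank-based version of the same adjusted model. Keep the unadjusted test now in G2 as a sensitivity analysis.

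**G1.** No change to the sample size is needed for this point.

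**Cost.** One question, one case report form field and a few lines in G2. The downside is that the gain may be small: many young or medicated children cannot give a useful score, and charted substitutes will vary in timing and analgesic state.

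### The postoperative rescue rule states no analgesic for a child whose score is exactly 4 before any score above 4, although a child at 2 or 3 is given an oral opioid

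*Combined protocol and SAP*

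**What the plan says.** F2 (Procedure) measures postoperative pain on a "verbal rating scale where 0 = no pain and 10 = worst possible pain ever", so 4 is an attainable score. It then states two rescue rules:

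- IV morphine: "patients with pain scores >4 will be treated with morphine 0.05mg/kg IV at 10 minute intervals until the score is below 4".
- The oral opioid combination (acetaminophen plus hydrocodone): this "will be administered to children for pain scores between 2-3".

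The next sentence of F2 leaves supplemental oxygen, antiemetics and antipruritics to local practice and the anesthesiologist's judgment. It does not mention analgesics.

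G2 (Data Analysis) lists "Opioid consumption in morphine equivalents" and "Time to first analgesia request" among the secondary endpoints. Its comparison paragraph words the second one differently: "time to first analgesia and discharge readiness and satisfaction scores will be compared between the two groups". G1 (Sample Size) also speaks of time to first analgesia, without the word request, when it claims 90% power for a 75% increase.

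**The concern.** The oral band ends at 3 and the IV band begins above 4. Read literally, the rule for a child not yet on morphine is not monotone in pain: a 4 leads to less analgesia than a 2 or a 3. Either a child at 4 goes without a protocol analgesic while children in less pain receive one, or staff decide for themselves what to do.

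That discretion reaches the endpoints. Section D describes the comparator as standardized postoperative systemic analgesia, and a rule that is silent at one score is not standardized there. Opioid consumption is the direct product of the bands. Time to first analgesia depends on them too if it means the first analgesic given, because the score rule is the only postoperative analgesic trigger that the protocol describes. If it means the first request, the link is weaker.

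**Working it through.** **1. The plan's own figure.** G1 states: "A group size of 34 would have an 80% power of detecting a clinically relevant difference in the peak pain scores of 2", with a significance level of 0.05 and an SD of 2.9 in both groups. Taking a two-sided test (sidedness is not stated):

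n per group = 2 × (1.960 + 0.8416)² × 2.9² / 2² = 2 × 7.849 × 2.1025 = 33.0, just above 33, so 34 after rounding up.

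The two-sample t-test solution is 33.99, also 34. Power by t-test is 80.0% at 34 per group and 86.1% at the planned 40. The figure reproduces, and the rescue bands do not enter it.

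**2. The rule applied to each score.** I assume that scores are whole numbers and apply the two F2 sentences as written, once before any score above 4 and once during morphine titration.

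| Score | Not yet on morphine | Already being titrated |
|---|---|---|
| 0–1 | none stated | morphine stops |
| 2–3 | oral opioid | morphine stops; oral band applies |
| 4 | **none stated** | morphine repeated |
| 5–10 | morphine starts | morphine repeated |

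The right-hand column has an action at every score. The left-hand column has a hole at 4, between two bands that both lead to an opioid.

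**3. Search for text that fills the hole.** The discretion sentence in F2 covers oxygen, antiemetics and antipruritics only. The fentanyl left to the attending anesthesiologist is intraoperative. The ketorolac given to all patients belongs to the anesthetic and does not respond to a score. No other section states an analgesic for a score of 4.

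**4. An illustration of how common a 4 might be.** G1 gives a control peak PACU score with mean 2.8 and SD 2.9 but no distribution, so the shape is an assumption. A beta-binomial on 0–10 respects the limits of the scale:

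- proportion m = 2.8 / 10 = 0.28
- binomial variance = 10 × 0.28 × 0.72 = 2.016
- variance ratio = 2.9² / 2.016 = 8.41 / 2.016 = 4.172
- ρ = (4.172 − 1) / 9 = 0.352
- α + β = 1/ρ − 1 = 1.838, so α = 0.515 and β = 1.323
- P(peak = 4) = 0.075; 0.075 × 40 = 3 control children

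This describes peak scores. The gap concerns any 4 reported before a score above 4, which is a different quantity. A child who peaks at 4 may already have had the oral opioid at 2 or 3. A child who passes through 4 on the way to a higher score is not counted.

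**5. Effect on the secondary endpoints.** This cannot be calculated. G1 gives no baseline mean or SD for time to first analgesia, and the document gives no variance for opioid consumption.

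**The case against.** The strongest reply is that this is one boundary score, probably a drafting slip, in a rule introduced as current practice. F2 says when drugs will be given; it does not forbid treating a 4. That is fair, and it means the text does not order analgesia to be withheld. It still leaves the action at 4 unstated in a rule meant to be standardized.

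Three stronger readings are tempting, and the documents support none of them.

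- *The start and stop cut-offs contradict each other.* A reader might infer this because morphine starts above 4 but stops only below 4. Starting above a level and continuing until the score is below it is a coherent titration rule, and it may be deliberate. That a 4 is handled differently before and during titration is not in itself an error. The asymmetry does not, however, explain the gap between the oral and IV bands.
- *The gap biases the comparison.* A reader might reason that staff who notice a numb arm would treat a 4 differently. The bands are identical in both arms, the data-collecting observer is absent when the block is placed, and every child gets the same dressing. The document does not say whether treating staff are blinded, but that question applies at every score. Nothing shows a direction of bias arising from this gap.
- *Up to 13% of children are affected.* A normal curve with mean 2.8 and SD 2.9 does put 12.6% between 3.5 and 4.5. It also puts about 13% below −0.5, which is impossible on this scale, and it describes peak scores only.

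It also stands that F2 already has the observer record each additional drug, its dose and its time, so most of the data needed are already collected.

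**Conclusion.** The point holds within limits. For a child who has not yet scored above 4, F2 states no analgesic at exactly 4, while 2 or 3 leads to an oral opioid, and no other section closes the gap. This follows from the text and needs only the assumption of whole-number scores.

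The consequence is avoidable untreated pain or unplanned discretion. Discretion adds noise to opioid consumption. It adds noise to time to first analgesia only under the G1 and comparison-paragraph wording (first analgesic), and less clearly under the endpoint-list wording (first request). No directional bias is shown, and the primary sample size stands.

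The size of the effect on either endpoint is unknown. The 7.5%, or about 3 of 40 control children, rests on an assumed beta-binomial shape for peak scores. It shows only that a 4 is not a rare value. The point is worth correcting because the change costs almost nothing, not because it threatens the main conclusion.

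**What to change.** - The clinical team should reconcile the two rescue sentences in F2 so that every whole score from 0 to 10 leads to one stated action, both before and during titration. The values, and any difference between the start and stop cut-offs, are theirs to decide.
- Add the triggering pain score to the case report form, beside the drug, dose and time already documented.
- Use one definition of time to first analgesia in G1 and G2, either first analgesic given or first request, so that its dependence on the rescue rule is clear.

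The cost is one protocol paragraph and one form field, plus agreement on the wording of that endpoint. No change to the sample size or the primary analysis follows.
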